7.10.2. Distribution of Subject Reminder Cards

Subjects will be provided with subject reminder cards at each visit. The subject reminder cards will indicate the date and time of the next visit. The reminder cards will have a field for the subject to enter the date and time of the last dose taken before the visit and to record the time of the last meal before applicable visits as per [Table 8](#), [Table 11](#), [Table 14](#), [Table 17](#), and [Table 20](#). Reminder cards will include instructions specific for the study visits, including for visits where the subject will refrain from taking the study drug at home in the morning before the clinic visit. All necessary instructions, such as those for study drug administration, concomitant medications, and laboratory tests should be provided to the subject in writing on this reminder card or on accompanying written materials.

8. SAFETY MONITORING AND REPORTING

8.1. Adverse Events

8.1.1. Definitions

For the purposes of this Protocol, an adverse event (AE) is defined as the appearance of or worsening of any pre-existing undesirable sign, symptom, or medical condition that occurs after a subject provides informed consent. Abnormal laboratory values or test results occurring after informed consent constitute AEs only if they induce clinical signs or symptoms, are considered clinically meaningful, require therapy (eg, hematologic abnormality that requires transfusion), or require changes in the study drug(s).

8.1.2. Reporting

Adverse events that begin or worsen after informed consent should be recorded on the Adverse Events form of the eCRF. Conditions that were already present at the time of informed consent should be recorded on the Medical History form in the eCRF. Monitoring for the occurrence of new AEs should be continued for at least 30 days after the last dose of study drug. Adverse events (including laboratory abnormalities that constitute AEs) should be described using a diagnosis whenever possible rather than by individual underlying signs and symptoms. When a clear diagnosis cannot be identified, each sign or symptom should be reported as a separate AE.

"Disease progression" should not be recorded as an AE itself unless there are no other identifiable AEs associated with the disease progression at the time of reporting. For events associated with disease progression, the relevant signs and symptoms should be reported using a diagnosis whenever possible rather than individual underlying signs and symptoms. When a clear diagnosis cannot be identified, each sign or symptom should be reported as a separate AE. If the events resulting from disease progression meet the criteria for an SAE (eg, resulted in hospitalization, a life-threatening event, or death), the specific event(s) should be reported as an SAE(s) as described in Section 8.3.2. In both cases (ie, AEs or SAEs related to disease progression), it should be indicated that each event (reported as a diagnosis or as signs and symptoms) is related to disease progression on the Adverse Events form of the eCRF.

Adverse events will be assessed according to the CTCAE v4.03. The CTCAE Grade 5 severity (death) will not be used in this study; rather, AEs with an outcome of death will be reported as CTCAE Grade 4, with an outcome of "fatal." Adverse events leading to death will be recorded with the outcome of the event as "fatal." If an event is not classified by CTCAE, the severity of the AE will be graded according to the scale below to estimate the grade of severity:

Grade 1	Mild; asymptomatic or mild symptoms; clinical or diagnostic observations only; intervention not indicated.
Grade 2	Moderate; minimal, local, or noninvasive intervention indicated; limiting age-appropriate activities of daily living.
Grade 3	Severe or medically significant but not immediately life-threatening; hospitalization or prolongation of hospitalization indicated; disabling; limiting self-care activities of daily living.
Grade 4	Life-threatening consequences; urgent intervention indicated.

CONFIDENTIAL

CONFIDENTIAL

The occurrence of AEs should be sought by nondirective questioning of the subject during the screening process after signing the ICF and at each visit during the study. Adverse events may also be detected when they are volunteered by the subject during the screening process or between visits, or through physical examination, laboratory test, or other assessments. To the extent possible, each AE should be evaluated to determine the following:

- The severity grade (CTCAE Grade 1 to 4).
- Whether there is at least a reasonable possibility that the AE is related to the study treatment: suspected (yes) or not suspected (no).
- The start and end dates, unless unresolved at final follow-up.
- The action taken with regard to study drug.
- The event outcome (eg, not recovered/not resolved, recovered/resolved, recovering/resolving, recovered/resolved with sequelae, fatal, unknown).
- The seriousness, as per SAE definition provided in Section 8.3.1.

Unlike routine safety assessments, SAEs are monitored continuously and have special reporting requirements (see Section 8.3.2).

All AEs should be treated appropriately. Concomitant medication or nondrug therapy used to treat an AE should be recorded on the Adverse Event form as well as the Prior/Concomitant Medications or Procedures and Non-Drug Therapy form in the eCRF.

Once an AE is detected, it should be followed until it has resolved or until it is judged to be permanent; assessment should be made at each visit (or more frequently if necessary) of any changes in severity, the suspected relationship to the study drug, the interventions required to treat it, and the outcome.

When the severity of an AE changes over time for a reporting period (eg, between visits), each change in severity will be reported as a separate AE until the event resolves. For example, 2 separate AEs will be reported if a subject has Grade 1 diarrhea, meeting the definition of an AE, which lasts for 3 days before worsening to a Grade 3 severity. The Grade 1 event will be reported as an AE with a start date equal to the day the event met the Grade 1 AE definition and a stop date equal to the day that the event increased in severity from Grade 1 to Grade 3. The Grade 3 event will also be reported as an AE, with the start date equal to the day the event changed in intensity from Grade 1 to Grade 3 and a stop date equal to the day that the event either changed severity again or resolved. For analysis purposes, this will be considered 1 AE for this subject and the maximum severity will be used.

8.2. Laboratory Test Abnormalities

Laboratory abnormalities that constitute an AE in their own right (considered clinically meaningful, induce clinical signs or symptoms, require concomitant therapy, or require changes in study drug) should be recorded on the Adverse Event form in the eCRF. Whenever possible, a diagnosis rather than a symptom should be provided (eg, "anemia" instead of "low hemoglobin"). Laboratory abnormalities that meet the criteria for AEs should be followed until they have returned to normal or an adequate explanation of the abnormality is found. When an abnormal

CONFIDENTIAL

CONFIDENTIAL

laboratory test result corresponds to a sign or symptom of a previously reported AE, it is not necessary to separately record the laboratory test result as an additional event.

Laboratory abnormalities that do not meet the definition of an AE should not be reported as AEs. A Grade 3 or 4 (severe) AE does not automatically indicate an SAE unless it meets the definition of serious, as defined in Section 8.3.1, and/or per the investigator's discretion. A dose modification for the laboratory abnormality may be required (see Section 5.2.3.1) and should not contribute to the designation of a laboratory test abnormality as an SAE.

8.3. Serious Adverse Events

8.3.1. Definitions

An SAE is defined as an event that meets at least 1 of the following criteria:

- Is fatal or life-threatening (ie, immediate risk of dying).
- Requires inpatient hospitalization or prolongation of existing hospitalization, unless hospitalization is a result of:
 - A routine treatment or monitoring of the studied indication not associated with any deterioration in condition.
 - An elective or preplanned treatment for a pre-existing condition that is unrelated to the indication under study and has not worsened since signing the ICF.
 - A treatment on an emergency outpatient basis for an event not fulfilling any of the definitions of a SAE given above and not resulting in hospital admission.
 - Any social reasons and respite care, in the absence of any deterioration in the subject's general condition.
 - Any SAEs that are expected due to the condition being treated, including if the SAE is a primary outcome measure, or where there has been a clear agreement with regulators not to consider these as SAEs, provided the information is collected elsewhere.
- Results in persistent or significant disability or incapacity.
- Constitutes a congenital anomaly or birth defect.
- Is clinically meaningful (ie, defined as an event that jeopardizes the subject or requires potential medical or surgical intervention to prevent 1 of the outcomes listed above).
- Is considered to be an important medical event or a medically significant event that may not result in death, be immediately life-threatening, or require hospitalization but may be considered serious when, based upon appropriate medical judgment, the event may jeopardize the subject or may require medical or surgical intervention to prevent 1 of the outcomes listed above.

CONFIDENTIAL

CONFIDENTIAL

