adverse events (SAEs) reported in 20 subjects (59%), 9 of which were considered related to study drug as per investigator assessment. The most common SAEs reported of any causality were febrile neutropenia (21%) and pneumonia (15%), while the most common SAEs reported as related to study drug were maculopapular rash (9%), ALT increased (6%), and AST increased (6%).

As of 31 DEC 2016, 6 of 34 subjects continue to receive study drug; 28 of 34 subjects permanently discontinued treatment (20 because of disease progression, 3 because of an AE, 2 because of death, 2 because of subject decision, and 1 because of physician decision). Seventeen subjects have died as of the cutoff date (12 from disease progression, 3 from unknown causes, 1 from disease-related intracerebral hemorrhage, and 1 from disease-related pneumonia/sepsis).

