2.2. Study Endpoints

2.2.1. Primary Endpoint

- Safety and tolerability will be assessed by monitoring frequency, duration, and severity of AEs and DLTs; through physical examinations; by evaluating changes in vital signs and electrocardiograms (ECGs); and through clinical laboratory blood and urine sample evaluations.
- Part 4 only: ORR, defined as the proportion of subjects who achieve complete remission (CR) or complete remission with incomplete hematologic recovery (CRi).

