8.3.2. Reporting

To ensure subject safety, every SAE, regardless of suspected causality, occurring after the subject has signed the ICF and up to the last study visit, or up to 30 days after the subject has stopped study treatment, whichever is later, must be reported to the sponsor (or designee) within **24 hours** of learning of its occurrence. Any SAEs occurring more than 30 days after the last dose of study drug should be reported to the sponsor, or its designee, only if the investigator suspects a causal relationship to the study drug. Recurrent episodes, complications, or progression of the initial SAE must be reported as a follow-up to the original episode within 24 hours of the investigator receiving the information. An SAE occurring at a different time interval or otherwise considered completely unrelated to a previously reported SAE should be reported separately as a new event. Previously planned (ie, before providing informed consent) surgeries should not be reported as SAEs unless the underlying medical condition worsens over the course of the study.

Information about all SAEs is collected and recorded on the Adverse Event form of the eCRF. The investigator must assess and record the causal relationship of each SAE to the study treatment.

The investigator must also complete the Incyte Serious Adverse Event Report Form, in English, and send the completed and signed form to the sponsor or designee within 24 hours of becoming aware of the SAE. The investigator must provide a causality assessment, that is, assess whether there is at least a reasonable possibility that the SAE is related to the study treatment: suspected (yes) or not suspected (no). Refer to the Incyte Reference Guide for Completing the Serious Adverse Event Report Form.

The contact information of the sponsor's study-specific representatives are listed in the investigator manual provided to each site. The original copy of the SAE Report Form and the confirmation sheet must be kept at the study site.

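### Section 8.3.1 takes hospitalizations for disease-expected events out of the SAE definition without listing those events, and this conflicts with Section 8.1.2

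*Protocol*

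**What the plan says.** Protocol Section 8.3.1 calls an event serious if it meets at least one of several criteria. One is hospitalization: "Requires inpatient hospitalization or prolongation of existing hospitalization, unless hospitalization is a result of" any of five listed reasons. The first four are conventional: routine care of the indication without deterioration, elective or preplanned treatment, emergency outpatient treatment without admission, and social or respite admissions. The fifth is "Any SAEs that are expected due to the condition being treated, including if the SAE is a primary outcome measure", and it continues "or where there has been a clear agreement with regulators not to consider these as SAEs, provided the information is collected elsewhere". The other criteria carry no such exemption. They include "Is fatal or life-threatening (ie, immediate risk of dying", disability, clinically meaningful events and important medical events.

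Section 8.1.2 deals with events caused by the disease: "If the events resulting from disease progression meet the criteria for an SAE (eg, resulted in hospitalization", a life-threatening event or death), they are to be reported as SAEs. Section 8.3.2 requires 24-hour reporting of "every SAE, regardless of suspected causality, occurring after the subject has signed the ICF".

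Table 4 in Section 5.2.3 states in its footnote that cytopenias and myelosuppression are expected in Part 1 TGA and in the Part 3 combination groups. Section 1.4.2 gives the Part 1 experience at the 31 DEC 2016 cutoff: 34 subjects enrolled, 20 (59%) with a treatment-emergent SAE, febrile neutropenia as an SAE in 21% and pneumonia in 15%.

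**The concern.** The fifth exemption does not work as an operating rule. It uses the term SAE to say what is not an SAE. It names no expected events, so each site makes its own list. Its proviso that the information be held elsewhere protects little: AEs go on the eCRF AE form in any case, no other form is named, and it is unclear whether the proviso covers the whole item or only the regulator-agreement part.

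Two outputs are at stake: the speed of reporting and the SAE counts. Section 8.1.2 has seriousness recorded by the definition in 8.3.1, so an exempted admission is entered as a non-serious AE. It then bypasses the 24-hour form and moves from the serious to the non-serious tables planned in SAP Section 10.2.5.

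This matters most in the AML combinations. Section 1.4.4 says the combination safety profiles are unknown. Table 4 makes febrile neutropenia not applicable as a hematologic DLT in C-TGA and C-TGB, and Section 8.2 says that Grade 3 or 4 alone does not make an event serious. Section 8.7 provides no formal data monitoring committee. SAE reporting is therefore an important formal alert for excess febrile neutropenia.

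**Working it through.** **The conflict, with the two sections side by side.** Take a subject admitted for a complication of progressing disease that is neither fatal nor life-threatening.

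1. Under Section 8.1.2, admission is a named example of meeting the SAE criteria, so the event is reported as an SAE.
2. Under the fifth exemption in Section 8.3.1, an admission for an event expected from the disease does not meet the hospitalization criterion. A complication of progression is a clear case of such an event.
3. Unless another criterion applies, the two sections give opposite answers.

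**Reproducing the Part 1 figures** (Section 1.4.2, N = 34), using the whole-number count that rounds to each stated percentage:

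- Any SAE: 20/34 = 58.8%, stated as 59%.
- Febrile neutropenia: 7/34 = 20.6%, stated as 21%.
- Pneumonia: 5/34 = 14.7%, stated as 15%.

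All three reproduce.

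**Bounding the effect.** Suppose every febrile neutropenia and pneumonia SAE were left out.

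- Subjects with at least one of the two: from 7 (all five pneumonia subjects also had febrile neutropenia) to 7 + 5 = 12 (no overlap).
- No overlap and no other SAE in these subjects: 20 − 12 = 8, or 8/34 = 23.5%.
- Full overlap and no other SAE: 20 − 7 = 13, or 13/34 = 38.2%.
- All of them had another SAE: 20/34 = 58.8%, unchanged.

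Subjects with any SAE would thus number 8 to 20 of 34. This range brackets an extreme case and is not an estimate. The documents do not say how many of these events were serious by hospitalization alone, and only those could drop out.

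**The case against.** The strongest reply is that the exemption narrows one route only. An event needs to meet just one criterion, and febrile neutropenia or pneumonia needing inpatient care can often qualify as clinically meaningful or as an important medical event. This stands. A reader might infer that the exemption removes the trial's commonest SAEs; the text supports only that it can remove some of them. The remaining routes do rest on judgment, so they reduce the site dependence without ending it. Support for calling these events expected is also uneven: the Table 4 footnote covers cytopenias, and no current text says that pneumonia is expected.

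A reader might also infer that, because "Safety and tolerability will be assessed by monitoring frequency, duration, and severity of AEs and DLTs" is the primary endpoint, the phrase about primary outcome measures exempts any AE. That is not the natural reading. The phrase is introduced as an inclusion within condition-expected events, and toxicity attributed to a study drug is not due to the condition.

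Nor is Section 8.3.2 contradicted. It governs events that already meet the definition, and an exempted event does not. Section 8.1.2 is itself conditional on the SAE criteria being met, but it offers hospitalization as an example of meeting them for disease events, and the exemption withdraws that example.

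Finally, the information is not lost. Section 8.7 provides weekly or biweekly subject-by-subject teleconferences and periodic AE review, and SAP Section 10.2.5 tabulates all TEAEs and Grade 3 or 4 TEAEs whatever their seriousness. This also stands, and it confines the loss mainly to 24-hour reporting and SAE counts.

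**Conclusion.** The point holds as a faulty stated rule of moderate consequence. The exemption is circular, lists no events and conflicts with Section 8.1.2. As written, it lets a site leave a hospitalized, disease-expected event out of 24-hour SAE reporting and the SAE tables when no other criterion is met. The size is unknown. The 8 to 20 of 34 range assumes that every febrile neutropenia and pneumonia SAE is dropped, and it varies with overlap and with other SAEs in the same subjects.

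Two further inferences are not supported:

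- **About half of subjects with SAEs could go unreported.** Section 1.4.2 says 9 were considered related to study drug. Reading that as subjects gives 20 − 9 = 11, and 11/20 = 55%. But unrelated to study drug does not mean expected from the disease, and the figure also needs all 11 to have been serious by hospitalization alone, which is not stated.
- **Parts 3 and 4 are not comparable with Part 1.** Febrile neutropenia and pneumonia were reported as SAEs in Part 1, but the documents do not show which wording of 8.3.1 applied then. The visible entries in Appendix T list no change to that section, though some entries are redacted. A shift in definition or practice is possible but not shown.

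**What to change.** Delete the fifth exemption from Section 8.3.1 and keep the other four, so that the section agrees with 8.1.2. If a regulator has agreed a specific exemption, replace the item with a list of the exempt preferred terms and require those events still to be recorded as serious on the eCRF AE form, so that the SAE tables remain complete.

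The cost is one deletion in an amendment, a memo to sites and somewhat more SAE forms, chiefly from sites treating AML. No analysis or sample size changes.

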8.3.2. Reporting

To ensure subject safety, every SAE, regardless of suspected causality, occurring after the subject has signed the ICF and up to the last study visit, or up to 30 days after the subject has stopped study treatment, whichever is later, must be reported to the sponsor (or designee) within **24 hours** of learning of its occurrence. Any SAEs occurring more than 30 days after the last dose of study drug should be reported to the sponsor, or its designee, only if the investigator suspects a causal relationship to the study drug. Recurrent episodes, complications, or progression of the initial SAE must be reported as a follow-up to the original episode within 24 hours of the investigator receiving the information. An SAE occurring at a different time interval or otherwise considered completely unrelated to a previously reported SAE should be reported separately as a new event. Previously planned (ie, before providing informed consent) surgeries should not be reported as SAEs unless the underlying medical condition worsens over the course of the study.

Information about all SAEs is collected and recorded on the Adverse Event form of the eCRF. The investigator must assess and record the causal relationship of each SAE to the study treatment.

The investigator must also complete the Incyte Serious Adverse Event Report Form, in English, and send the completed and signed form to the sponsor or designee within 24 hours of becoming aware of the SAE. The investigator must provide a causality assessment, that is, assess whether there is at least a reasonable possibility that the SAE is related to the study treatment: suspected (yes) or not suspected (no). Refer to the Incyte Reference Guide for Completing the Serious Adverse Event Report Form.

The contact information of the sponsor's study-specific representatives are listed in the investigator manual provided to each site. The original copy of the SAE Report Form and the confirmation sheet must be kept at the study site.

Investigational site personnel must report any new information regarding the SAE within 24 hours of becoming aware of the information in the same manner that the initial SAE Report Form was sent. Follow-up information is recorded on an amended or new SAE Report Form, with an indication that it is follow-up to the previously reported SAE and the date of the original report. The follow-up report should include information that was not provided on the previous SAE Report Form, such as the outcome of the event (eg, resolved or ongoing), treatment provided, action taken with study drug because of the SAE (eg, dose reduced, interrupted, or discontinued), or subject disposition (eg, continued or withdrew from study participation). Each recurrence, complication, or progression of the original event should be reported as follow-up to that event, regardless of when it occurs.

If the SAE is not documented in the IB for the study drug (new occurrence) and is thought to be related to the sponsor's study drug, the sponsor or its designee may urgently require further information from the investigator for reporting to health authorities. The sponsor or its designee may need to issue an Investigator Notification (IN) to inform all investigators involved in any study with the same drug that this SAE has been reported. Suspected Unexpected Serious Adverse Reactions (SUSARs) will be collected and reported to the competent authorities and relevant ethics committees in accordance with Directive 2001/20/EC, or as per national regulatory requirements in participating countries.

CONFIDENTIAL

CONFIDENTIAL

